### **5.2 Subjects Randomized and Discontinued Prior to 10 NOV 2015- (Pre-Administrative Hold Population)**

On November 10, 2015, COL MIG-305/H8H-CD-LAHL was stopped per the FDA due to not filing the protocol prior to initiating enrollment. Subjects were advised to not dose a migraine and were asked to return to the clinic to be discontinued. The study was initiated with FDA approval on November 13, 2015. The study was amended to outline the process for the subjects to be discontinued from the study and then be allowed to restart the study if they wished. In summary subjects undergo an End-of-Study visit as outlined and if they are interested in participating in the study they are re-consented and then re-randomized. The data from all subjects enrolled in the period October 7, 2015 to November 10, 2015 will be maintained in the database and reported in

the clinical study report as a subset of the overall study.

Data generated during this period is not included in the randomized population, the safety population, or the ITT populations. Data from this period will be analysed separately and be limited to subject demographics, disposition, exposure, adverse events, and serious adverse events.

### **5.3 Addendum 1 and Addendum 2 Subjects**

With the addition of these two addenda to Study 305/LAHL, additional subjects could be randomized after August 2016. The visit structure and procedures for this set of subjects are different from those for subjects that came from the parent studies. Therefore, observations that serve as baseline are different from those specified throughout this document. For this group of subjects, baseline will be defined as either Visit 0 or Visit 1, depending on when information is collected, and still represents observations prior to any study medication dosing. Other differences for this group of subjects includes the ability to dose migraines with baseline severity of ‘Mild’, the ability to dose a migraine up to 8 hours of its onset, and subjects that are lasmiditan-naïve.

As these differences in protocol procedures are not anticipated to effect safety or efficacy endpoints, for all analyses, these subjects will be incorporated into the previously defined subject populations. Additionally, a listing of randomized subjects that were added to the study based on Addendum 1 or Addendum 2 will be provided.

The database lock in May 2018 will not include patients added to the study through these addenda.

### **5.4 Analysis of First and Second Doses**

Any analyses based on first dose will only include data observed up to the time of dosing with a second dose. These summaries will be presented based on the first dose taken. The exception to this is the secondary endpoints at the 2-hour time point; if a second dose is taken before the 2-hour time point, the subject will still be included in the summary at 2 hours and will be analysed as having not achieved headache pain-free or MBS-free status at 2 hours.

Any analyses based on the second dose will only include data observed on or after the time of dosing with a second dose. Analyses based on the second dose will be done for both the rescue and recurrence subpopulations.

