8. STUDY DRUG MATERIALS AND MANAGEMENT

8.1 Study Drug

Study drug refers to lasmiditan 100 mg and lasmiditan 200 mg.

Lasmiditan drug product is a tablet containing 100 mg or 200 mg of lasmiditan (as free base). The tablet is white, film coated, and round with no markings. Lasmiditan drug product is for oral administration.

CCI

Each dose of study drug will consist of one tablet for the treatment of a single migraine attack. For subjects randomized to lasmiditan 100 mg, a second dose may be used for treatment of recurrence of migraine between 2 and 24 hours after the first dose. For subjects randomized to lasmiditan 200 mg, no additional study drug is to be taken within 24 hours of the dose, as the maximum dose of lasmiditan to be taken in a 24-hour period is 200 mg.

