### **5.5 Handling of Missing Values**

Subjects who fail to record information at a particular analysis time point will have that value considered missing in the respective table, unless otherwise specified.

The endpoints of headache severity and MBS presence at 2 hours post-dosing are two exceptions to this: (1) Subjects who fail to record a headache severity at 2 hours for each treated migraine

will be assumed to have not achieved headache pain-free status, and (2) subjects who fail to record the absence of a symptom at 2 hours at each treated migraine that was considered their MBS at baseline will be assumed to have not achieved MBS-free status. This will be considered for data presented for each treated migraine attack.

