### **11.1 Efficacy analysis of secondary endpoint**

For the secondary endpoint the proportion of attacks treated with lasmiditan 100 mg and with lasmiditan 200 mg which respond as headache pain-free at 2 hours will be calculated for each 3 month period based on the treated migraine-level of the mITT population.

The proportion will be calculated as number of attacks which meet the criteria for headache pain-free at 2 hours divided by total number of treated attacks in each treatment group.

This analysis will be presented by treated migraine attack for total no. of attacks in each treatment group. This data will be presented for each three month period of time such as 0 – 3 months after randomization, > 3 – 6 months after randomization, > 6 – 9 months after randomization, > 9 – 12 months after randomization as well as for the entire study.

Headache pain-free is defined as a reduction in headache severity from mild (1), moderate (2), or severe (3) at baseline to none (0).

Treated migraines that do not have a headache pain severity rating at baseline will be excluded from the analysis. Treated migraines that do not have an associated headache pain severity rating at the two-hour time point will be assumed to have not achieved headache pain-free.

Subjects taking any rescue medication within the first two hours will be assumed to have not achieved headache pain-free. Subjects who use other medication prior to the study drug to treat the migraine attack will also be assumed to have not achieved headache pain-free.

Subjects who treat a no (0) severity migraine will not be included in this analysis.

Similar analysis will also be performed for Most Bothersome Symptoms Free at 2 hours post dose and Headache Pain Relief at 2 hours post dose under the same assumptions of sections 11.2.1.2 and 11.2.1.6 .

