## **11.2 Efficacy analysis of additional endpoints**

### **11.2.1.1 Headache Pain-Free**

The endpoint of headache pain-free will be summarized in proportion at the 0.5, 1, 2, 4, 24, and 48-hour post-dose time points. This summary will be presented by treatment group for the ITT and mITT populations, based on first dose and for ITT2nd dose rescue and recurrence population based on second dose. These presentations will be summarized on ITT and mITT treated migraine level analysis.

Treated migraines with a mild, moderate, or severe headache severity at the time of dosing will be

the reference subjects for this summary. Treated migraines without a headache severity at baseline, or with a headache severity of 'none' will be excluded. Treated migraines missing a severity assessment at a post-dose time point will not be categorized as pain-free.

This data will be summarized for the 1st, 2nd, 3rd, 4th, 5th, 10th, 15th, and 20th treated migraine.

Similarly, data will be presented for subjects with only moderate or severe pain at dosing for mITT Population at treated migraine level.

For subjects that treated 5 or more migraines, headache pain-free at 2 hours will be summarized across the first five treated migraines and as overall response for all treated migraines. Overall response for each subject in this subgroup is calculated by dividing the number of successful responses (responses at 2 hours) by total number of attacks treated.

Additionally, a time to headache pain-free Kaplan-Meier analysis will be conducted on the first treated migraine for the subject-level ITT population by dose.

Summary of headache pain free will be presented for all treated migraine attacks for mITT population as overall numbers and by each quarter as defined in section 8.5.

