### **11.2.1.3 Sustained Headache Pain Free**

Sustained pain-free response will also be summarized at the 24 and 48-hour post-dose time points in the same tables of Headache pain free for listed populations in section 11.2.1.1

Sustained Pain-Free is defined as experiencing headache pain-free at two hours after first dose and at the subsequent indicated assessment time, having not used any medications after the first dose for each treated migraine.

This data will be summarized for the 1st, 2nd, 3rd, 4th, 5th, 10th, 15th, and 20th treated migraine.

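### After 2 hours, a second lasmiditan dose and other acute medication are handled by different rules in the first-dose efficacy summaries, which can distort the 4, 24 and 48 hour rates by dose

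*SAP*

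**What the plan says.** **Display.** SAP 11.2.1.1: "The endpoint of headache pain-free will be summarized in proportion at the 0.5, 1, 2, 4, 24, and 48-hour post-dose time points", by treatment group. Sections 11.2.1.2 (MBS-free) and 11.2.1.6 (relief) use the same time points.

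**Second lasmiditan dose.** SAP 5.4: "Any analyses based on first dose will only include data observed up to the time of dosing with a second dose". Its one exception concerns re-dosing that happens too early, short of 2 hours: "the subject will still be included in the summary at 2 hours and will be analysed as having not achieved headache pain-free". SAP 5 adds that the diary cancels the remaining first-dose alarms once a second dose is reported.

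**Missing later ratings.** For pain-free, SAP 11.2.1.1: "Treated migraines missing a severity assessment at a post-dose time point will not be categorized as pain-free". Section 11.2.1.6 does the same for relief. Section 11.2.1.2 instead omits an attack from any time point at which its symptoms are missing. The general default in SAP 5.5 is that an unrecorded value "will have that value considered missing in the respective table, unless otherwise specified".

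**Other medication.** SAP 11.1: "Subjects taking any rescue medication within the first two hours will be assumed to have not achieved headache pain-free". Medication taken before study drug is also a failure. Section 11.2.1.2 has the same 2-hour limit on rescue. Nothing covers other medication taken later. Protocol 5.4 has subjects who use it continue the diary to 48 hours.

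**Sustained pain-free.** SAP 11.2.1.3 requires "having not used any medications after the first dose for each treated migraine", which covers both kinds of treatment.

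**Who may re-dose.** Protocol 7.3.2 allows a second dose for recurrence in the 100 mg arm only, and Protocol 8.1 says: "For subjects randomized to lasmiditan 200 mg, no additional study drug is to be taken within 24 hours of the dose". SAP 2.1 describes second doses in both arms, for rescue or recurrence, and Protocol 4.5 still refers to a second dose of either strength for both purposes.

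**The concern.** Needing more treatment after the first dose is one clinical event, and these summaries treat it in opposite ways according to the drug used. If the subject takes lasmiditan again, first-dose data stop and the attack cannot be a responder. If the subject takes another drug, the diary runs on, and a rating of no pain at 24 hours counts as a first-dose response.

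Under Protocol 7.3.2 and 8.1 this is tied to arm. A recurrence within 24 hours may be re-dosed in the 100 mg arm, but any drug treatment of it in the 200 mg arm must be something else. The same recurrence can then count against 100 mg and in favour of 200 mg. SAP 11.2.1.1, 11.2.1.2 and 11.2.1.6 also show results by quarter. If attacks were treated under different second-dose rules during the study, as the amendment rationale in Protocol Appendix 6 indicates, a change of rule could look like a change in response over time.

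Even with no difference between arms, the later rates partly describe other drugs.

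**Working it through.** The plan states no re-dosing, rescue or response rates after 2 hours, so there is no figure to reproduce. All rates below are assumptions. True response is set equal in the two arms, so any difference comes from the scoring.

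**Symbols**
- m: share of attacks given more acute treatment after 2 hours and before the time point
- s: share of those treated with a second lasmiditan dose (s100, s200 by arm)
- q: share pain-free at the time point after other medication
- p0: share pain-free among attacks with no further treatment, set at 0.70

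**Reading A: a re-dosed attack stays in the denominator as not achieved** (SAP 11.2.1.1 and 11.2.1.6).
- P = (1 - m)p0 + m(1 - s)q
- P200 - P100 = m × q × (s100 - s200)

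**Reading B: a re-dosed attack leaves the denominator** (SAP 11.2.1.2, and what the exception in SAP 5.4 suggests).
- P = [(1 - m)p0 + m(1 - s)q] / (1 - m × s)
- With s100 = 1 and s200 = 0: P200 - P100 = m(q - p0)

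**Extreme case, s100 = 1 and s200 = 0**

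| m | q | A: 100 mg | A: 200 mg | A: difference | B: 100 mg | B: 200 mg | B: difference |
|---|---|---|---|---|---|---|---|
| 0.10 | 0.50 | 63.0% | 68.0% | +5.0 | 70.0% | 68.0% | -2.0 |
| 0.20 | 0.60 | 56.0% | 68.0% | +12.0 | 70.0% | 68.0% | -2.0 |
| 0.30 | 0.70 | 49.0% | 70.0% | +21.0 | 70.0% | 70.0% | 0.0 |

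Over a wider range (m 0.05-0.30, q 0.30-0.90), Reading A runs from 0.05 × 0.30 = +1.5 to 0.30 × 0.90 = +27.0 points. Reading B runs from 0.30 × (0.30 - 0.70) = -12.0 to 0.30 × (0.90 - 0.70) = +6.0, so the sign can reverse.

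**Less extreme cases, Reading A, for the three rows above**
- s100 = 0.5, s200 = 0: +2.5, +6.0, +10.5 points.
- s100 = 0.8, s200 = 0.6: a factor of 0.2, giving +1.0, +2.4, +4.2 points.
- s100 = s200: zero, on either reading.

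**Under the recurrence-only rule.** Attacks not pain-free at 2 hours use other medication in both arms (Protocol 7.3.1), so they cancel. What remains on Reading A is q times the share of all 100 mg attacks that are re-dosed recurrences: 0.5 to 0.7 points for each 1% of attacks re-dosed, with q of 0.50-0.70. At 4 hours only recurrences re-dosed between 2 and 4 hours contribute.

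**With one rule.** At m = 0.20 and q = 0.60, scoring any further medication as not achieved gives 0.80 × 0.70 = 56.0% in both arms. Using outcomes regardless of further treatment would give 56.0% + 0.20 × 60% = 68.0% in both, if q also holds after a second dose.

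**The case against.** The strongest objection is that SAP 5.4 nowhere calls a second dose a failure after 2 hours. It makes inclusion at 2 hours the exception, SAP 5.5 defaults to missing, and SAP 5.7 leaves affected first-dose assessments out of the summaries in its items on retroactive entry and partial second-dose times. On that view re-dosed attacks leave the later summaries. This stands in part. For MBS-free, SAP 11.2.1.2 says so directly. For pain-free and relief, the specific rules in 11.2.1.1 and 11.2.1.6 point the other way, and the SAP does not settle the denominator. Dropping re-dosed attacks while crediting those given another drug is still unequal handling.

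A reader might infer that the plan biases the dose comparison towards 200 mg by 5-21 points. The documents do not support that. The figure needs every further treatment in the 100 mg arm to be a second dose and none in the 200 mg arm, whereas under Protocol 7.3.1 rescue is other medication in both arms. If both arms re-dose equally, as they could under the SAP's description, the artefact is zero. If re-dosed attacks are dropped, it can favour either arm.

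The stakes are also limited. Safety is primary, the secondary endpoint is at 2 hours, efficacy is descriptive, and no efficacy test of 200 mg against 100 mg is planned. Sustained pain-free appears in the same tables with a uniform rule, and SAP 8.5 tabulates second doses and other medication after 2 hours. These points lower the weight of the concern but do not remove it: sustained pain-free also requires freedom from pain at 2 hours, so it does not replace the simple rates.

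**Conclusion.** The inconsistency is real. In first-dose summaries at 4, 24 and 48 hours, a second lasmiditan dose ends the data, and the attack is either not categorized as a response or dropped, depending on the endpoint. Other medication after 2 hours has no rule, so later good ratings are credited to lasmiditan.

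Distortion between doses is possible, not demonstrated. Under Protocol 7.3.2 and 8.1 it is confined to recurrences and falls mainly at 24 and 48 hours. On assumed rates of 10-30% further treatment and 50-70% pain-free afterwards, 5-21 points is an upper bound. It becomes 2.5-10.5 points if half of the 100 mg arm's further treatment is a second dose, and zero with equal re-dosing. Direction also depends on the unstated denominator. The 2-hour secondary endpoint and sustained pain-free are unaffected. This should be corrected because it changes reported rates and is cheap to settle, but it touches only descriptive additional endpoints.

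**What to change.** In SAP 5.4, 11.2.1.1, 11.2.1.2 and 11.2.1.6, state one rule for first-dose summaries after 2 hours: once any further acute medication is taken, whether a second lasmiditan dose or another drug, the attack counts as not achieved from that time and stays in the denominator. This carries over the any-medication condition of SAP 11.2.1.3. Using outcomes regardless of further treatment would also be uniform, but it is hard to apply because the diary restarts its schedule from the second dose.

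Show the use of each kind of further treatment by arm and time point beside these rates.

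The SAP and protocol passages on who may take a second dose, and for what, must be reconciled. The SAP should also say how attacks treated under different second-dose rules are pooled.

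The cost is SAP wording and programming, and the later rates will be lower. Protocol 9.1.8.1 records the date and time of rescue medication. Protocol 7.3.2 says only that medication for recurrence is recorded, so confirm that its time is captured too.

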### **5.5 Handling of Missing Values**

Subjects who fail to record information at a particular analysis time point will have that value considered missing in the respective table, unless otherwise specified.

The endpoints of headache severity and MBS presence at 2 hours post-dosing are two exceptions to this: (1) Subjects who fail to record a headache severity at 2 hours for each treated migraine

will be assumed to have not achieved headache pain-free status, and (2) subjects who fail to record the absence of a symptom at 2 hours at each treated migraine that was considered their MBS at baseline will be assumed to have not achieved MBS-free status. This will be considered for data presented for each treated migraine attack.

### **5.6 Analysis for Final Database Lock**

All the analysis for the final database lock will be similar to the interim analysis lock (May 2018), such that the same tables, listings and figures will be provided. Analyses for the pre-administrative hold population were conducted for the interim analysis lock (May 2018) and therefore will not be included in the final lock. Apart from those all patients including addendum 1 and 2 will be included in the final analysis.

### **5.7 Derivation of Diary Assessment Times for Efficacy and Exploratory Analysis**

The secondary and additional exploratory endpoints along with second-dose exploratory analysis endpoints will be summarized at various elapsed times following dosing for each treated migraine attack. The endpoints will depend on data collected by an e-diary that requires a subject's response entries in the correct order and at the expected, scheduled assessment times. These assessment times are calculated by the e-diary from elapsed time since dosing. (They will not be recalculated as a part of analysis programming.) The e-diary poses questions to be answered within a pre-specified window of elapsed time after dosing. There will be some scenarios when responses appear to have been limited by the e-diary programming, if questions are not answered in the expected order or during the programmed window, which may cause unscheduled data at some time points.

Unscheduled data can be defined as invalid data at time points which do not correspond to the actual dosing data at the intended time point entered by subject. Listed are some examples of unscheduled data:

1. When subject takes 2nd dose but due to subject's response to the timing of dosing question in e-diary, the e-diary does not understand that subject took 2nd dose, but continues to collect the first dose time points because they are still 'valid' based on subject's entry. Thereby second dose questions do not become available until the time points align. In this case, the data for first dose is unscheduled.
2. Due to subject's responses to e-diary questions, e-diary assumes that subject took 2nd dose at one-time point but subject indicate dosing at a different time point. This makes their second dose data unscheduled but often keeps first dose data from being unscheduled.

3. Due to subject's responses to e-diary questions, e-diary assumes that subject took 2nd dose but subject indicates not dosing as per study drug accountability and CRF confirmation so 2nd dose data will be unscheduled.

Some specific scenarios are listed below for derivation of analysis time points for efficacy and exploratory endpoints.

1. Retroactive dose entry. If a subject enters the time of a dose retroactively, rather than at the time of taking the dose, the recorded time, and potentially date, of the second dose may be before some or all of the scheduled times of assessments that would otherwise have appeared to be associated with the first dose. In those cases, the apparent first-dose assessments after the recorded time of the second dose, and the second-dose assessments at times calculated from the retroactively entered dosing time will not be included in efficacy analyses.
2. Reports intention to take second dose, without confirmation. Subjects report their intention to take a second dose but may not *confirm* having done so in e-diary. Even if indications of taking second dose are observed in e-diary data, until the entry shows confirmation of second dose times, the e-diary will not have a confirmed second-dose time from which to calculate post-dose assessment times after that second dose, and it will not switch to second-dose mode. In this state, second-dose assessments will be missing. Additionally e-diary continues to collect first dose data although the subject may have taken second dose. Even if use of a second dose is recorded on the on CRF, the related second-dose assessments may not be available in the e-diary because the e-diary is not working in second-dose mode; hence, the exploratory endpoints for second dose will not be available at those analysis times. Additionally, first dose assessments collected after this time will be considered unscheduled.
3. Multiple reports of a migraine - complicated by aura. If a subject reports a migraine, but does not indicate taking first dose at a specific time due to presence of aura, the efficacy and exploratory analysis endpoints for first and second dose will be summarized for the migraine, which has the reference for most recent available treated migraine data at analysis time points.
4. Subjects reporting migraine start time or dosing time in future in e-diary. If a subject reports a migraine start time in the future and if the time reported is less than one hour in the future, this will be considered as minor minute or hour entry issues and the migraine start time will be set as time of collection. The remaining time issues will be assumed on visual confirmation as AM/PM (midnight/noon) and PM/AM (yesterday/today) entry issues then these will be rolled back by increments of 12 hours until the time is before time of data collection. After these corrections if migraine start

is still after dosing time then the migraine start time is set to dosing time. These subjects will be included in the appropriate populations of efficacy analysis with these assumptions.

1. Similarly for subjects who report a first dose time with start in the future (by several hours) than indicated dosing with question “Treating Migraine with Study Med now” as “Y” at the migraine pain begin time, their efficacy assessments for first dose will be those many hours ahead of the actual assessment time for severity reporting. For example, e-diary’s 0.5 hour time point is actually 7.5 hours if the first dose time is after 7 hours of the reported migraine start time. If the reported dose time is less than 10 minutes than the time of reporting migraine as in the stated question, then these will be ignored and subject’s efficacy assessments will be used for appropriate populations of efficacy analysis. All other subjects with time difference of greater than 10 minutes will be excluded from the appropriate populations of efficacy analysis.
5. Subjects with partial second dose time on CRF and no e-diary date and time for second dose Subjects who are able to enter the first dose assessment data in e-diary but they are not able to complete the e-diary for second dose. These subjects will be able to give second dose confirmation date on the CRF at site for visit 2 but may not remember the time of the dosing for second dose after first dose. These subjects will be considered in the appropriate populations of efficacy analysis for first dose available assessments based on the assumption that they took the second dose after the minimum of 2 hours post first dose. For these subjects any assessments for first dose data after 2 hours will be unscheduled and not be summarized.

Efficacy analysis: Below assumptions will be considered for determining the start and end dates for treatment exposure.

- a. If CRF dates data is matched with e-diary dates and times: The start and end of treatment exposure for analysis will always be identified from the first and last dates of dosing entered in the CRF, when available and appear to match the e-diary dosing data.
- b. If CRF dates data is NOT matched with e-diary dates and times: The e-diary screens for post dose assessments entered by subjects are auto-generated by the e-diary at times with respect to dosing dates and times entered in the e-diary. As a result of this e-diary function, these subjects will be included in ITT populations of efficacy analysis when there is a confirmation of such dosing on CRF, within a reasonable matching timeframe with e-diary. Such as CRF treatment start dates

(+12 hours) will be matched if they are minimally within 24 hours of e-diary first or second dose dates.

- c. If CRF dosing dates are available but e-diary dosing information is missing: If the first dose is reported taken in the CRF with the appropriate date entered in CRF but the subject did not complete the e-diary for assessments, then the date of first dose and associated assessments will be missing in e-diary data. These subjects will not be included in ITT efficacy analysis due to unavailability of efficacy assessment data.
- d. If CRF dosing dates are missing but e-diary dosing information is available: It will be determined that these subjects have not visited at sites (or even they have lot of follow-up) and there is no confirmation on exact dosing on CRF. These subjects will be excluded from Efficacy analysis.

